3 STUDY OBJECTIVES AND DESIGN

3.1 Primary objective and hypothesis

Quantification of physical activity (daily steps) during the first two weeks after hospital discharge as a predictor for MACE at one year.

Hypothesis I: Daily steps measured during the first two weeks after hospital discharge from PCI is a significant independent predictor additional to traditional risk factors for MACE at one year after PCI.

Secondary objectives and hypothesis

1. Comparison between daily steps and objectively measured activity counts (divided in time spent in moderate-to-vigorous activity, light activity and sedentary activity), as well as patient reported activity:

Hypothesis I: Objectively monitored activity counts two weeks after hospital discharge is significantly associated with daily step counts and self-reported activity level

Hypothesis II: Predictive value of daily step count during the first two weeks after hospital discharge is significantly better than the predictive value by patient reported physical activity for MACE at 12 months.

2. Association of daily steps after one year with reaching targets for systolic blood pressure, low-density lipoprotein cholesterol (LDL-C), body mass index (BMI) and glycated haemoglobin (HbA1c):

Hypothesis I: Patients with higher daily step counts during the first two weeks after hospital discharge have higher achievement rates of target levels at 12 months for blood pressure, body weight, blood lipids, and blood sugar.

3. Comparison of daily steps after hospital discharge and MACE between non cardiac rehabilitation (CR), conventional hospital based CR, tele-CR and modular CR participants.

Hypothesis I: Tele-rehabilitation and conventional CR patients achieve higher daily step counts (corrected for age, risk factors and comorbidities) at two weeks after PCI than patients who decline any form of CR.

Hypothesis II: Tele-rehabilitation and conventional CR patients a lower risk of MACE within one year than patients who decline any form of CR

4. Comparison of daily steps at one year after hospital discharge in different CR groups.

Hypothesis I: Tele-rehabilitation is not inferior to conventional ambulatory cardiac rehabilitation (CR) in increasing daily steps from two weeks after PCI to 12 months after PCI

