3.2 Primary and secondary endpoints

Primary endpoint: Occurrence of MACE within 12 months after PCI

Secondary endpoints: BMI, systolic BP, LDL-C, HbA1c and daily steps two weeks and 12 months after PCI; proportion and patient characteristics of CR participants and non-participants

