4.2 Recruitment, screening and informed consent procedure

Consecutive patients who are eligible for ambulatory CR are seen by the prevention team (nurse practitioners) usually on the day of hospital discharge from PCI and will be informed about the different forms of CR and the study.

All eligible patients will be provided a participant information sheet and a consent form describing the study and providing sufficient information for participants to make an informed decision about their participation in the study. The participants can consider their participation and decide upon participation during the first week after hospital discharge. Additionally to the patient information sheet and the IC form, the activity tracker in the form of a wrist band, the IPAQ-SF and an addressed and prepaid envelope will be handed out before hospital discharge. They are asked to read the patient information when arrived at home, sign the IC when willing to participate and wear the wrist band continuously for two weeks after hospital discharge. After that, they should send the wrist band, filled-in IPAQ-SF and signed IC in the provided envelope to our institute.

Each participant will be informed that if they lose the activity tracker or it is lost with the mail, they are not held reliable for the loss. Each participant will be informed that the participation in the study is voluntary and that he or she may withdraw from the study at any time and that withdrawal of consent will not affect his or her subsequent medical assistance and treatment.

The participant will be informed that his or her medical records may be examined by authorised individuals other than their treating physician.

The formal consent of a participant, using the approved consent form, will be signed by the participants at home and sent back with the questionnaire and activity tracker. The participants are not submitted to any study procedures other than wearing the activity tracker.

The consent form will be signed and dated by the investigator or his designee when the form arrives at the Inselspital. A copy of the signed informed consent will be sent back to the study participant. The consent form will be retained as part of the study records.

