5 STATISTICS AND METHODOLOGY

5.1. Statistical analysis plan and sample size calculation

Predictive value of daily steps during the first two weeks after hospital discharge is quantified by net reclassification improvement (NRI) and by increase of area under the curve (AUC) of the receiver operating characteristic curve (ROC) of a model consisting of traditional risk factors (age, sex, cardiovascular risk factors, cardiovascular history, comorbidities).

Descriptive statistics are used to quantify and characterise the populations who choose conventional hospital based CR, tele-rehabilitation, and modular CR in terms of number, age, sex, medical history, cardiovascular risk factors and comorbidities. MACE at one year follow-up and daily steps during the first two weeks after hospital discharge will be compared between the CR and non CR participants using multivariate modelling adjusted for potential confounding factors. Further, for patients who perform their yearly routine follow-up visit at our centre, data on body mass index (BMI), systolic blood pressure (BP), low-density lipoprotein cholesterol (LDL-C) and smoking cessation will be derived from the clinic's patient information system and compared between different forms of CR. Also, daily steps after 12 months from patients who volunteer to monitor steps again will be quantified for the different CR groups and tested between the groups if sufficient data can be gathered. The same will be done for changes in daily steps between the first two weeks after hospital discharge and at 12 months.

Sample Size:

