8 QUALITY CONTROL AND DATA PROTECTION

8.1 Quality measures

Nurses of the prevention team at the Department of Cardiology, Inselspital, will be trained in how to inform patients about this study and provide them with the study information and IC-form. Further, corresponding with routine clinical practice at the Inselspital, they will inform patients about the three different forms of CR and will recruit patients for CR. Data from activity trackers will be downloaded from devices upon their return from patients and uploaded into Redcap by

appropriately trained personnel at the unit for Preventive Cardiology and Sports Medicine of the Inselspital.

For quality assurance the sponsor, the Ethics Committee or an independent trial monitor may visit the research sites. Direct access to the source data and all study related files is granted on such occasions. All involved parties keep the participant data strictly confidential.

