8.2 Data recording and source data

Data from the activity trackers will be downloaded and stored in Redcap. Questionnaires on physical activity will be manually entered into Redcap.

At the end of the study, data from this study will be merged with data from Cardiobase PCI registry, namely data on patient anthropometrics, cardiovascular history, indication for and interventions of the index PCI, comorbidities and cardiovascular risk factors, and MACE at one year follow-up. Data on choice of CR and compliance with CR and health related data will be available from the clinical data base of the unit for Preventive Cardiology and Sports Medicine of the Inselspital.

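### Section 5.1 compares one-year MACE by CR participation while Hypothesis 3.II compares against patients who decline CR; if participation is used, MACE before CR entry biases the result in favour of CR

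*SAP*

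**What the plan says.** The SAP describes the two groups in several ways.

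- **Section 5.1, analysis of MACE and early steps:** these outcomes "will be compared between the CR and non CR participants using multivariate modelling adjusted for potential confounding factors". No landmark, time-dependent exposure or rule for a MACE before CR entry is given.
- **Section 3.1, secondary objective 3, Hypothesis II:** "Tele-rehabilitation and conventional CR patients a lower risk of MACE within one year than patients who decline any form of CR".
- **Section 3.2:** the primary endpoint is "Occurrence of MACE within 12 months after PCI", so the clock starts at PCI. A secondary endpoint is the "proportion and patient characteristics of CR participants and non-participants".
- **Section 5.1, descriptive part:** the aim is to "characterise the populations who choose conventional hospital based CR, tele-rehabilitation, and modular CR".
- **Sections 4.2 and 8.1:** patients are seen "usually on the day of hospital discharge from PCI and will be informed about the different forms of CR". Of the nurses, 8.1 says that "they will inform patients about the three different forms of CR and will recruit patients for CR".
- **Section 8.2:** "Data on choice of CR and compliance with CR and health related data will be available". Both the choice and the compliance are therefore to hand, and the SAP does not say which one forms the MACE groups.

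**The concern.** Choice of CR can be known at discharge, before nearly all of the follow-up. Participation is known only later, and a patient has to reach CR entry to be counted as a participant. Take someone who agreed to CR and had a MACE before the first session that kept them out. Under Hypothesis 3.II this patient is not a refuser. Under a literal reading of 5.1 the patient is not a participant either, and so falls into the non-CR group together with the event.

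Each such patient takes an event out of the CR group and adds one to the comparator. The error runs in the direction that Hypothesis 3.II predicts. Adjusting for age, risk factors and comorbidities does not help, because the fault lies in assigning exposure from information that arises after the clock has started, and not in an imbalance of baseline characteristics.

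There is a second mismatch in the same contrast. Hypothesis 3.II names only tele-CR and conventional CR, whereas 5.1 pools CR and lists modular CR among its forms.

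**Working it through.** **The plan's own figures.** Section 5.1 needs 33 events for a hazard ratio of 2.66, two-sided 5%, 80% power and equal groups: 4 × (1.960 + 0.842)² / (ln 2.66)² = 32.8, rounded up to 33. Doubling gives 66 events, and 66 / 0.08 = 825 patients. These figures reproduce. They size the primary objective; the SAP gives no figure for Hypothesis 3.II. I use 825 and 66 only as a scale.

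**Assumptions not in the SAP.** No true CR effect; flat hazard; uptake u = 50%; a share m of the MACE before entry prevents CR (m = 1 or 0.5). Two entry days are tried:

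- Day 14, because Appendix 1 mentions a CR entry examination in what appears to be the day 1-14 column.
- Day 36, the mean time after PCI or CABG in a cohort cited in section 2 (part on step/activity counts during CR), whose title places it at CR entry.

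MACE is counted from PCI (section 3.2) or from day 7 (the window behind the 8% in section 5.1).

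**Formula.** With f the share of the year's MACE that falls before entry:

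moved = 66 × f × u × m

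RR = [(66u − moved) / (825u − moved)] / [(66(1−u) + moved) / (825(1−u) + moved)]

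**Example:** day 36, counted from day 7, m = 1. f = 29/358 = 8.1%; moved = 66 × 0.081 × 0.5 = 2.67; RR = (30.33/409.83) / (35.67/415.17) = 0.0740/0.0859 = 0.861.

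| Entry | MACE from | f | m | Moved | Spurious RR |
|---|---|---|---|---|---|
| Day 14 | PCI | 14/365 = 3.8% | 1 | 1.27 | 0.932 |
| Day 14 | PCI | 3.8% | 0.5 | 0.63 | 0.965 |
| Day 14 | Day 7 | 7/358 = 2.0% | 1 | 0.65 | 0.965 |
| Day 14 | Day 7 | 2.0% | 0.5 | 0.32 | 0.982 |
| Day 36 | Day 7 | 29/358 = 8.1% | 1 | 2.67 | 0.861 |
| Day 36 | Day 7 | 8.1% | 0.5 | 1.34 | 0.928 |

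Over 40 to 60% uptake, the day-14 range widens to 0.916 to 0.985. Counting from PCI with entry at day 36 lowers the ratio further (f = 36/365 = 9.9%, m = 1, u = 50%: 0.833).

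**Against sampling error.** SE(log RR) = √[2 × (1/33 − 1/412.5)] = 0.236, so 95% limits around a ratio of 1 are 0.63 to 1.59. The chance of a significant result in favour of CR when there is no effect is Φ(−1.96 − ln RR / 0.236), against a nominal 2.5%:

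- RR 0.982: 3.0%
- RR 0.932: 4.8%
- RR 0.928: 5.0%
- RR 0.861: 9.2%

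**Under the alternative groupings.** If status is the choice at discharge, no patient moves and RR = 1 under no effect. In a simulation of the day-14 scenarios (8% risk, no effect, 50% uptake), grouping by choice gave 0.997 to 0.999, a day-14 landmark gave 0.998 to 1.000, and grouping by participation gave 0.931 to 0.982.

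**The case against.** The strongest reply is that the SAP uses its terms loosely and means the choice made at discharge. Objective 3 says participants in its heading and decline in its own Hypothesis II. The sentence at issue in 5.1 directly follows the one about patients who choose a form of CR. Section 2 speaks of enrolling, and section 4.1 makes not enrolling in stationary CR an eligibility criterion, which Appendix 1 has the nurses check at discharge. The reference to participants in 3.2 concerns their proportion and characteristics, not MACE. This reading is plausible, but the text does not fix it: the synopsis draws on CR uptake, and 8.2 offers compliance alongside choice. Two analysts could build different groups from this plan.

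The second reply is that the size is assumed throughout. That stands. Day 14 is inferred from a table cell about where a questionnaire is filled in. Day 36 comes from another cohort that included CABG patients. The SAP never says that a MACE stops CR entry, and patients who enter CR after an early event would reduce the bias.

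Third, 825 and 66 describe patients willing to wear the tracker for two weeks, who return consent afterwards. An event inside those two weeks may also prevent return, so in that population the day-14 bias would be smaller. This stands too.

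Two stronger inferences are tempting. A reader might conclude that a biased, participation-based analysis is firmly planned; the wording on choosing, declining and recruitment around discharge does not support that. A reader might also take a definite size from the table, whether negligible or large. Neither is supported, because entry time, uptake and the share of early MACE that prevents CR are not in the document.

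**Conclusion.** The mismatch between 5.1 and Hypothesis 3.II is real. So are the mechanism and the direction if 5.1 is followed literally: MACE before CR entry counts against the non-CR group, this favours CR, and the planned adjustment cannot correct it. If groups are formed by the choice at discharge, this bias is absent.

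The size is open. It should not be called slight, since that label depends on entry within about two weeks. Nor do the figures show a dominant effect: under the assumptions in the table, about 0.3 to 2.7 of 66 events change group, and even a ratio of 0.86 lies well inside the 95% sampling limits.

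Severity is minor. One non-randomised secondary comparison is affected, section 3.3 calls the study explorative, and the primary analysis of steps and MACE is untouched.

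**What to change.** Add to section 5.1 that, for the MACE comparison, CR status is the choice or refusal recorded at the discharge visit, in line with Hypothesis 3.II, with MACE counted from PCI. In the same place, say whether modular CR belongs to the CR group.

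If actual participation is intended, there are two options:

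- **Landmark:** fix status at a stated day among patients MACE-free at that day, and count only later MACE.
- **Time-dependent exposure:** treat CR as starting on its start date, if start dates are recorded. Section 8.2 does not mention them.

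The cost is a sentence or two, plus confirmation from the sponsor that the choice is recorded at discharge. Each option has a price. Grouping by choice dilutes a true effect of participating. A landmark loses a few early events (at day 14 under a flat hazard, 66 × 2.0% = 1.3 to 66 × 3.8% = 2.5) and counts later starters as non-CR.

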Endpoint(s)	Primary endpoint: MACE at one year after PCI. Secondary endpoints: BMI, systolic BP, LDL-C, HbA1c 12 months after PCI; daily steps and activity level two weeks and 12 months after PCI hospital discharge; proportion and patient characteristics of CR participants and non-participants
Study Design	Observational single centre study.
Statistical Considerations	Predictive value of daily steps during the first two weeks after hospital discharge is quantified by net reclassification improvement (NRI) and by increase of area under the curve (AUC) of the receiver operating characteristic curve (ROC) of a model consisting of traditional risk factors (age, sex, cardiovascular risk factors, cardiovascular history, comorbidities).
Inclusion- / Exclusion Criteria	Inclusion criteria: Patients after PCI younger than 80 years of age who are eligible for ambulatory CR. Exclusion criteria are inability to participate in ambulatory CR (nursing home residence, stationary CR, orthopedic or neurologic impairment prohibiting physical exercise, psychiatric conditions), and staged PCI.
Number of Participants with Rationale	The sample size is based on a previous study who found a significant difference between the quartile with lowest versus highest self-reported physical activity on MACE at 3 years after PCI. Based on this, we would need 33 events to reach a significance level of 0.05 and a power of 80% in these two quartiles or 66 events in the whole sample. According to data from CARDIOBASE Bern PCI registry, we can expect 100 MACE per year in approximately 1200 patients younger than 80 years of age undergoing PCI at our centre. If we assume that

	50% of these patients are willing to participate in our study, we could recruit about 800 patients in 16 months, who will have approximately 66 MACE within one year.
Study Intervention	Patients will be provided with an activity tracker in the form of a wrist band that they should wear continuously for two weeks after hospital discharge. After 12 months, they will be asked to wear the activity tracker again for two weeks in case they attend the clinical routine check-up in our institution.
Control Intervention	None

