4 STUDY POPULATION AND STUDY PROCEDURES

4.1 Inclusion and exclusion criteria, justification of study population

Approximately 800 consecutive patients after PCI who are informed about different forms of CR are recruited for this study.

Study inclusion criteria:

- 18-79 years of age;
- eligible for ambulatory CR (not living in nursing home, not enrolling in stationary CR).

Exclusion criteria:

- Staged PCI;
- previous participation in this study;
- inability or contraindications to undergo CR (nursing home residence, stationary CR, orthopedic or neurologic impairment prohibiting physical exercise, psychiatric conditions)
- inability to follow the procedures of the study, e.g. due to language problems, psychological disorders, dementia, etc..

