Based on a study on nearly 9000 PCI patients, physical activity level assessed by the Duke Activity Status Index (DASI) questionnaire found a 4.8-fold increase in future risk of incident major adverse cardiac events at 3 years in the quartile with lowest DASI compared to the highest quartile.(6) The DASI score reclassified 15% of patients ($P<0.001$) beyond traditional risk factors in predicting future MACE.(6) In the approximately 6500 patients with obstructive CAD, the adjusted HR (adjusted for traditional risk factors and history of heart failure and peripheral arterial disease) for MACE in the lowest DASI quartile compared to the highest quartile was 2.66 (95% CI 2.16 to 3.27). According to this relative hazard, 33 events would be needed to reach a significance level of 0.05 and a power of 80% in these two quartiles. For the whole sample this would be 66 events. According to data from CARDIOBASE, in the 10 years from 2009-2018 1083 (8%) of patients younger than 80 years had a MACE between 7 and 365 days after PCI, which corresponds to approximately 100 MACE per year. During the last 3 years (Oct 2015 to Oct 2018), 3683 patients younger than 80 years were recruited for CARDIOBASE, which equates to approximately 1200 potential study patients per year. If we assume that 50% of these patients are willing to participate in our study (wear an accelerometer for 2 weeks after discharge), we could recruit about 600 patients per year, of whom approximately 48 (8%) will have a MACE within 12 months following PCI. To reach 66 MACE we will need to recruit 825 patients which will require

a recruitment period of approximately 16 months.

Statistical analyses will be performed by [name] (CAS in statistics of the University of Bern) using the software R.

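### The sample-size projection deducts nothing for ineligibility: 600 patients a year, 16 months and 66 events assume that every registry PCI patient under 80 can be enrolled

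*SAP*

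**What the plan says.** SAP section 5.1 builds the sample size in one chain.

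- **Effect.** From an earlier study of a self-reported activity score, the adjusted hazard ratio "for MACE in the lowest DASI quartile compared to the highest quartile was 2.66 (95% CI 2.16 to 3.27").
- **Events.** On that basis, "33 events would be needed to reach a significance level of 0.05 and a power of 80% in these two quartiles". Then: "For the whole sample this would be 66 events".
- **Event rate.** In CARDIOBASE, 2009 to 2018, "1083 (8%) of patients younger than 80 years had a MACE between 7 and 365 days after PCI".
- **Inflow.** From October 2015 to October 2018, "3683 patients younger than 80 years were recruited for CARDIOBASE", "which equates to approximately 1200 potential study patients per year".
- **Participation.** Half of these patients are assumed willing to wear the tracker. This gives 600 per year with 48 MACE, and 825 patients in about 16 months to reach 66 MACE.

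The synopsis uses the same base, patients under 80 having PCI at the centre, and concludes: "we could recruit about 800 patients in 16 months, who will have approximately 66 MACE within one year".

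Section 4.1 defines a narrower population. Patients must be eligible for ambulatory CR. Staged PCI and previous participation are excluded, as is "inability or contraindications to undergo CR (nursing home residence, stationary CR, orthopedic or neurologic impairment prohibiting physical exercise, psychiatric conditions"). Patients unable to follow the study procedures, for instance because of language problems or dementia, are excluded too. Section 4.2 confirms that the patients approached are those eligible for ambulatory CR.

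Section 4.3 sets recruitment at 16 months, from October 2020 to February 2022. The one extension tied to a shortfall, in section 5.2, applies when more than 50 patients are non-compliant with the tracker.

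**The concern.** Both registry inputs, the inflow and the MACE rate, come from patients filtered by age alone. The remaining section 4.1 criteria enter nowhere. The 50% factor does not stand in for them, because section 5.1 defines it as willingness and applies it to the whole 1200. An ineligible patient cannot be enrolled however willing, so the chain implicitly sets eligibility at 100%, which section 4.1 contradicts.

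At stake are the three figures on which feasibility and information rest: accrual rate, recruitment period and number of events. If the calendar ends recruitment, the primary objective is assessed on fewer events than planned. If the count of 825 governs, recruitment takes longer than stated. The section 5.2 extension responds to poor tracker wear, not to too few eligible patients or too few events.

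**Working it through.** **Inputs from the documents:** hazard ratio 2.66; alpha 0.05 and power 80%; MACE rate 8% (days 7 to 365); 3683 registry patients in 3 years; willingness 50%. Alpha is taken as two-sided, which the SAP does not state but which reproduces its figure.

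**Inputs not in the documents:** the share *e* of registry patients under 80 who meet section 4.1, and the MACE rate *r* among them. Both are assumed below.

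**1. Reproducing the plan.**
- Events in two equal groups (Schoenfeld): 4 × (1.96 + 0.84)² / (ln 2.66)² = 32.8, rounded up to 33.
- Whole sample: 2 × 33 = 66.
- Patients: 66 / 0.08 = 825.
- Inflow: 3683 / 3 = 1228 per year, taken as 1200.
- Accrual: 1200 × 0.50 = 600 per year, or 50 per month.
- Duration: 825 / 50 = 16.5 months (16.1 if 1228 is used).

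The arithmetic is sound, given *e* = 100% and *r* = 8%.

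**2. Slack at 100% eligibility.** 16 × 50 = 800 patients, and 800 × 0.08 = 64 events. The synopsis reaches 66 from 800 only by using 100/1200 = 8.33% (800 × 0.0833 = 66.7).

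**3. Eligibility below 100%, with *r* = 8% and willingness 50%.**
- Patients in 16 months = 800 × *e*; events = 64 × *e*.
- Months to 825 patients = 825 / (50 × *e*).
- Power on the plan's own two-quartile logic = Φ(ln 2.66 × √d / 2 − 1.96), where d is half the events.

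| Assumed *e* | Patients in 16 months | Events | d | Two-quartile power | Months to 825 |
|---|---|---|---|---|---|
| 100% | 800 | 64.0 | 32.0 | 79% | 16.5 |
| 90% | 720 | 57.6 | 28.8 | 75% | 18.3 |
| 75% | 600 | 48.0 | 24.0 | 67% | 22.0 |
| 60% | 480 | 38.4 | 19.2 | 57% | 27.5 |

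The power column restates the SAP's calculation with fewer events. It is not power for the net reclassification improvement (NRI) or the AUC increase, by which section 5.1 quantifies predictive value.

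**4. A different event rate (illustration only).** With the full 825 patients, *r* = 7%, 6% or 5% would give about 58, 50 or 41 events and two-quartile power of 75%, 68% or 60%. No figure in the SAP supports any of these rates.

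**5. What would offset ineligibility.** Uptake of 50% / *e* restores 800 patients: 62.5% at *e* = 80%, or 66.7% at *e* = 75%. The plan does not assume this.

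**The case against.** The strongest reply is that the SAP gives neither the eligible share nor the event rate among eligible patients, and that 50% is itself an unsupported round figure. What matters is eligibility times uptake, and higher uptake among eligible patients could restore the planned number. This stands as far as it goes. A reader might infer that the design cannot deliver 66 events in 16 months; the documents do not support that. They show that the projection omits a deduction its own criteria require, not how large the deduction is.

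A reader might also infer that the enrolled cohort must have a rate below 8%, because nursing-home residents and impaired patients are excluded. That is plausible but unsupported. Other exclusions, such as language problems, staged PCI and previous participation, have no documented direction of effect on MACE, and the 8% already leaves out the first days after PCI. The supportable statement is that 8% is not shown to apply.

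It is further true that if 825 patients is the binding target, ineligibility alone lengthens recruitment and costs no events. Section 5.1 gives a count and section 4.3 gives dates, without saying which prevails, so both consequences are shown above.

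Finally, section 3.3 calls the study explorative, and section 6.7 lists insufficient recruitment as a ground for early termination. Neither repairs the mismatch between the population counted and the population enrolled.

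**Conclusion.** The point holds for accrual. The stated 600 patients per year, 16 months and 66 events are consistent with section 4.1 only if every registry patient under 80 is eligible, and even then 16 months fall slightly short, at 64 events at 8%. With 50% willingness and 8% MACE held fixed, assumed eligibility of 90%, 75% or 60% reduces 16 months of recruitment to about 58, 48 or 38 events, or extends recruitment of 825 patients to about 18, 22 or 28 months. The direction follows from the plan's own inputs; the size rests on the assumed eligible share.

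For the event rate the conclusion is weaker: the 8% has not been shown to describe the eligible cohort, and results at other rates are illustrative. This should be corrected, but it is not an arithmetic error in the SAP.

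**What to change.** 1. Apply to the CARDIOBASE extract those section 4.1 criteria that it can identify, and use the unit's clinical database for choice of CR. Section 8.2 names both as data sources.
2. State the resulting eligible number per year and its MACE rate between days 7 and 365.
3. Apply the 50% willingness to that number. Alternatively, state explicitly that 50% is the product of eligibility and uptake, and justify it.
4. Restate recruitment duration, expected events and resulting power in the synopsis and section 5.1, and label the power as that of the two-quartile comparison.

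**Cost.** A small data extraction and revised text. Section 8.2 does not show that these sources can identify every exclusion; language problems, for example, would need a stated assumption. The restated figures will probably be less favourable. Restating them does not itself restore 66 events; that would need longer recruitment or higher uptake if eligibility proves materially below 100%.
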